6.6. Continued Access to Study Intervention After the End of the Study

Participants will be instructed that study intervention will not be made available to them after they have completed/discontinued study intervention and that they should return to their primary physician to determine standard of care.

Local regulations on continued access will always take precedence. Plans for continued access stated in this protocol may change if new information on the benefit-risk profile of guselkumab becomes available during the study or program.

6.7. Treatment of Overdose

For this study, any single dose of guselkumab greater than the highest dose planned (eg 400 mg for the cross over group) will be considered an overdose. The Sponsor does not recommend specific treatment for an overdose. As discussed in Section 10.4.4, overdose is a special reporting situation such that the event requires expedited reporting.

In the event of an overdose, the investigator or treating physician should:

- Contact the Medical Monitor (or designee) immediately.
- Evaluate the participant to determine, in consultation with the Medical Monitor (or designee), whether study intervention should be interrupted.
- Closely monitor the participant for AE/SAE and laboratory abnormalities.
- Document the quantity of the excess dose of the overdosing in the eCRF.

6.8. Concomitant Therapy

Concomitant therapies must be recorded throughout the study from signing of consent to the last study visit.

All concomitant therapies (prescription or over-the-counter medications, including vaccines, vitamins, herbal supplements) must be recorded in the eCRF. Recorded information will include the name of the medication, start and stop dates, and its reason for use.

6.8.1. Concomitant Conventional CD Medications

Standard immunomodulators (MTX, AZA, and 6-MP) or IV/oral corticosteroids should not be initiated (or increased in dose) unless medically necessary as rescue therapy as this will impact the efficacy analyses in this study and will be considered treatment failure (see the SAP for full treatment failure criteria). If initiated as rescue therapy, these treatments should be discontinued or tapered off as soon as medically tolerable and appropriate; however, participants can (and should) continue to receive study intervention and attend all study visits despite initiation (or increasing dose) of any of these CD related medications, except for those described as prohibited medications below (see Section 6.8.2).

6.8.1.1. Oral Corticosteroids

It is recognized that some participants will have been steroid dependent prior to their surgery and may be unable to safely complete tapering of their steroid therapy prior to randomization. However, as participants enter the study without residual active CD, participants who enter the study on steroids should initiate, or continue, tapering of corticosteroids for CD without any delay upon study entry at Week 0, unless medically inappropriate. Corticosteroid tapering should follow the below-recommended schedule (Table 2), without exceeding the prescribed magnitude or rate

of tapering unless due to medical necessity (eg, participant experiencing corticosteroid-related side effects).

If a participant experiences worsening in his/her disease activity while tapering corticosteroids, further dose decreases may be suspended, and the oral corticosteroid dose may be temporarily increased if deemed necessary by the investigator, to attempt to return to response. For participants whose corticosteroid taper is interrupted on this basis, investigators should resume tapering as soon as possible thereafter.

Table 2: Recommended Tapering Schedule for Oral Corticosteroids			
Recommended Tapering Schedule for Oral Corticosteroids (Other than Budesonide)			
Dose > 15 mg/day prednisone or equivalent	Taper daily dose by 5 mg/week until receiving 10 mg/day, then continue tapering at 2.5 mg/week until 0 mg/day		
Dose 11 to 15 mg/day prednisone or equivalent	Taper daily dose to 10 mg/day for 1 week, then continue at 2.5 mg/week until 0 mg/day		
Dose ≤ 10 mg/day prednisone or equivalent: Taper daily dose by 2.5 mg/week until 0 mg/day			
Recommended Tapering Schedule for Oral Budesonide			
Participants receiving budesonide should have their daily dose tapered by 3 mg every 3 weeks until 0 mg/day.			

If medically necessary (due to worsening disease or symptoms), participants may initiate oral corticosteroids if needed to manage their disease, but these should be discontinued and/or tapered off, as described above, as soon as clinically possible. The initiation of a physician-prescribed corticosteroid, or an increase in the dose of steroids already being taken (by greater than 5 mg/day), for over one week for the treatment of CD warrants further evaluation for clinical recurrence as described in Section 9.4.3.

6.8.2. Prohibited Concomitant Medications

In contrast to the concomitant medications described above, initiation of any of the following medications is prohibited (until the last study intervention administration at Week 144) and if initiated, should result in discontinuation from further study intervention, although such participants should not terminate study participation (unless enrolling in an interventional CD study or initiating a commercial anti-TNF, anti-IL-12 or 23, anti-IL 23 or anti-integrin biologicas described further below), and are encouraged to complete all visits through the next 12 weeks, at which point the mandatory early termination visit should be performed.

Immunomodulator agents other than AZA, 6-MP, or MTX (including but not limited to 6-thioguanine, cyclosporine, tacrolimus, sirolimus, mycophenolate mofetil, tofacitinib and other JAK inhibitors)

Note: As discussed in Section 6.8.1, AZA, 6-MP, MTX and corticosteroids may be initiated if medically necessary for rescue therapy, so their initiation does NOT necessitate discontinuation of study intervention.

- Immunosuppressant biologic agents, including but not limited to commercial TNF-antagonists (eg, infliximab, adalimumab, certolizumab), IL 12-23 inhibitors (ie, ustekinumab), IL-23 inhibitors (eg, risankizumab), integrin inhibitors (eg, natalizumab, vedolizumab), and abatacept
- Experimental or investigational CD medications

Note: Until the study treatment period is completed (ie, Week 152), participants must not receive commercial guselkumab outside of the protocol or participate in any other CD clinical study with an investigational agent while in this study. Further, participants must discontinue any further study intervention and also terminate study participation in these circumstances, with performance of the early termination visit prior to initiating these drugs. If the decision or realization that this is about to occur coincides with a scheduled visit, then the early termination visit should be performed in place of the scheduled visit, with the scheduling and performance of the follow-up ileocolonoscopy occurring as soon as possible. The rationale for handling initiation of these agents in this way is that subsequent efficacy and safety data in the context of the study would be uninterpretable.

As protection of human research participants is paramount, it is recognized that initiating these prohibited therapies may rarely be required due to medical necessity. However, initiation of the above prohibited medications prior to Week 152 should be documented as a deviation from the study protocol (unless study intervention has already been discontinued or completed), and participants must be discontinued from receiving further study intervention once these agents are started.

6.8.3. Vaccinations (including COVID-19)

When considering use of locally-approved (including emergency use-authorized) COVID-19 vaccines in study participants, consider protocol lifestyle considerations (Section 5.3) and follow applicable local vaccine labeling, guidelines, and standards of care for patients receiving immune-targeted therapy.

For study participants receiving a locally-approved (including emergency use-authorized) COVID-19 vaccine, in order to help identify acute reactions potentially related to the COVID-19 vaccine, it is recommended that, where possible, vaccine and study intervention be administered on different days, separated by as large an interval as is practical within the protocol.

7. DISCONTINUATION OF STUDY INTERVENTION AND PARTICIPANT DISCONTINUATION/WITHDRAWAL

7.1. Discontinuation of Study Intervention

A participant's study treatment should be discontinued if:

• The investigator or the medical monitor believes that for safety reasons (eg, an AE) it is in the best interest of the participant to stop treatment.

- The participant becomes pregnant or plans a pregnancy within the study period or within 12 weeks after the last study intervention administration.
- The participant meets **ANY** of the following TB related conditions:
 - A diagnosis of active TB is made.
 - A participant has symptoms suggestive of active TB based on follow-up assessment questions and/or physical examination or has had recent close contact with a person with active TB and cannot or will not continue to undergo additional evaluation.
 - A participant undergoing evaluation has chest imaging with evidence of current active TB and/or a positive IGRA test result, unless active TB can be ruled out and appropriate treatment for latent TB can be initiated prior to the next administration of study intervention and continued to completion.
 - A participant receiving treatment for latent TB discontinues this treatment prematurely or is noncompliant with the therapy.
- The participant has a serious adverse reaction that is related to an bronchospasm with wheezing and/or dyspnea that requires ventilatory support OR that results in symptomatic hypotension with a decrease in systolic blood pressure >40 mm Hg or blood pressure <90/60 mm Hg. In general, discontinuation of study intervention administration must be considered for participants who develop non-serious, but severe
- The participant develops a malignancy including squamous cell skin cancer. Consideration may be given to allow participants to continue to receive study intervention if they develop ≤2 basal cell skin cancers that are adequately treated with no evidence of residual disease.
- The initiation of the following protocol-prohibited medications at any time during the study as listed in Section 6.8.2.
- A serious opportunistic infection occurs.
- The participant (or the participant's representative) withdraws consent (or assent) for further administration of study intervention.
- The participant has CD-related surgeries that will preclude the future ability to assess efficacy through the CDAI. Surgeries that are thought to represent a lack of efficacy of study intervention should be considered for discontinuation at the discretion of the Investigator other than minor procedures (eg, placement of a seton or cutaneous drainage of an abscess).
- The participant has severe liver test abnormalities that are not transient and are not explained by other etiologies; see Section 10.7 for definitions of abnormal values.
- The participant reports suicidal ideation with intention to act ("Ideation level 4"), suicidal ideation with specific plan and intent ("Ideation level 5"), or any suicidal behavior (interrupted suicide attempt, aborted suicide attempt, or preparatory behaviors for making a suicide attempt) on a post-baseline C-SSRS assessment. If a participant can be adequately treated with psychotherapy and/or pharmacotherapy based on an evaluation by a mental health professional, then the participant, at the discretion of the investigator, may be continued with treatment if agreed to by the medical monitor or designee. Discussion of such participants with the medical monitor or designee is required.

• A participant who has crossed over to receive open-label treatment with guselkumab and is assessed not to have subsequently attained improvement, in the investigator's judgement (recommended to be initially assessed approximately 16-24 weeks after initiating open-label guselkumab treatment).

Participants who discontinue study intervention (for the reasons above) before the end of planned study treatment (Week 144), should not terminate their study participation (unless enrolling in an investigational advanced therapy CD study or initiating commercial guselkumab prior to cross over to open-label treatment, as described further below). Instead, participants discontinuing study intervention are encouraged to complete study visits through the next 12 weeks, at which time an early termination visit (see SoA, Section 1.3) must be performed. Should the early termination visit be due within 4 weeks of a regularly scheduled visit, it is appropriate to perform the procedures specified for the early termination visit at the appointed time in place of the regular scheduled visit.

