Participants who discontinue study intervention early will return for an early termination visit at least 12 weeks after study intervention discontinuation, which will also serve as their final safety visit. This visit will include a video ileocolonoscopy at the time of discontinuation, except those participants who have already had demonstrated endoscopic recurrence in a study ileocolonoscopy.

Study Length

After the screening period, the total study duration is 156 weeks, with the final dose of study intervention given at Week 144 and the final efficacy visit at Week 152 followed by the final safety visit at Week 156. The end of the study is defined as when all participants have completed the Week 156 visit assessments, or have terminated study participation prior to Week 156 and had their last follow-up assessment (12 weeks after the last dose of study intervention or at early termination visit).

The main study period is defined as when the last randomized participant has completed the Week 48 assessments at which point the main study database lock will occur. Participant follow-up for the main study period may vary depending upon when they enrolled in the trial (estimated to be from 12 to 30 months, based upon an anticipated accrual time of 18 months, but with an upper limit of 36 months [total study treatment duration], should accrual time exceed 18 months).

Endpoints

The primary endpoint is endoscopic recurrence prior to or at Week 48. Video ileocolonoscopy will be performed at the Week 48 visit and centrally read, using a definition of a modified Rutgeerts score of \geq i2a disease activity to define endoscopic recurrence.

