4.4. End of Study Definition

The end of study is considered as the Week 156 visit for the last participant in the study. The final data from the study site will be provided to the sponsor (or designee) after completion of the final participant Week 156 assessments at that study site, in the time frame specified in the Clinical Trial Agreement.

Participant Study Completion Definition

A participant will be considered to have completed the study if the participant has completed assessments at the Week 156 visit (including participants who crossed over).

Participants who prematurely discontinue study intervention for any reason before completion of the Week 144 study intervention administration can be considered to have completed the study if they have completed an early termination visit which should occur approximately 12 weeks after the last dose of study agent. This scenario includes participants who crossed over to open-label treatment and subsequently did not respond, precluding further continuation in the study.

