9.4.2. Primary Endpoint

The primary endpoint is endoscopic recurrence prior to or at Week 48 as defined by modified Rutgeerts score \geq i2a in the neo-terminal ileum, anastomotic site, or its equivalent elsewhere in the GI tract (eg, colonic ulceration).

Estimands and Estimators

Primary Estimand of Endoscopic Recurrence prior to or at Week 48

Treatment by Week 48:

Experimental: Guselkumab at Week 0 and then thereafter through the end of the total study period.

Control: Matched placebo at Weeks 0 and 8 and then the total study period.

i. Population:

Participants with recent (<49 days) qualifying surgery and no evidence of active Crohn's disease postoperatively.

ii. Variable (endpoint):

A binary recurrence variable (recurrence/no recurrence) where recurrence is defined as Endoscopic Recurrence prior to or at Week 48 (as defined by modified Rutgeerts score greater than or equal to i2a) or experiencing intercurrent events (ICEs) 1-4 presented below.

iii. Intercurrent events (ICEs) and corresponding strategies:

The following are the ICEs considered for this study:

- 1) A CD-related surgery (with the exception of minor procedures such as drainage of a superficial abscess or seton placement, etc.)
- 2) A prohibited change in CD medication
- 3) Discontinuation of study intervention due to lack of efficacy or an AE of worsening CD
- 4) Cross over to open-label guselkumab
- 5) Discontinuation of study intervention due to COVID-19 related reasons (excluding COVID-19 infection)
- 6) Discontinuation of study intervention due to reasons other than those in ICE 3 or 5

Intercurrent events in categories 1-4 will be handled by the composite strategy. The composite strategy assesses the treatment effects not only based on the variable measurements, but also based on ICEs. This estimand acknowledges that having an ICE in categories 1-4 is an unfavorable outcome. For participants experiencing ICEs in category 5 and 6, the treatment policy strategy will be used and considers the occurrence of ICE category 5 and 6 is irrelevant in defining the treatment effect and so observed values of the variable will be used, if available, regardless of the occurrence of ICE category 5 and 6.

iv. Population-level summary:

 Difference in proportions of the binary recurrence variable of endoscopic recurrence, as described above, between guselkumab group and the placebo group.

Estimators

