5. 6.	Discontinuation of study intervention due to COVID-19 related reasons (excluding COVID-19 infection) Discontinuation of study intervention due to reasons other than those in ICE 3 or 5	and any data observed after the associated ICE event will be used for the analysis

Abbreviation: AE=adverse event; CD=Crohn's disease; COVID-19= Coronavirus disease 2019; ICE=intercurrent event

20

Intercurrent events in categories 1-4 will be handled by the composite strategy. The composite strategy assesses the treatment effects not only based on the variable measurements, but also based on ICEs. This estimand acknowledges that having an ICE in categories 1-4 is an unfavorable outcome. For participants experiencing ICEs in category 5 and 6, the treatment policy strategy will be used and considers the occurrence of ICE category 5 and 6 is irrelevant in defining the treatment effect and so observed values of the variable will be used, if available, regardless of the occurrence of ICE category 5 and 6.

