5.3.3. Analysis Methods

5.3.3.1. Estimator (Analysis) of the Primary Estimand

The analyses will be based on the Full Analysis Set (FAS), which includes all randomized participants. Participants will be analyzed according to the intervention group to which they were randomized regardless of the study intervention they actually received.

To compare the guselkumab versus placebo group for the primary endpoint, the Cochran Mantel Haenszel chi-square test (2-sided) will be used with stratification of clinical remission status at baseline (CDAI < 150, CDAI \ge 150), region (North America, Western Europe, rest of world) and number of prior surgeries (1 surgery versus > 1 surgery, with the qualifying surgery counting as 1 surgery). The study will be considered successful if the test of the primary endpoint is positive at the 0.05 significance level.

After accounting for the ICE strategies, missing data will be imputed by multiple imputation.

Multiple imputation will be used for imputing missing data under the assumption that the data are MAR. The analysis will impute the missing Rutgeerts score at Week 48 using the analysis method and ancillary variables as described in Table 8. The responses at Week 48 will be derived from the imputed datasets and combined for analysis.

Variable	MI specification	Analysis method/Summary statistics
Rutgeerts score at Week 48	Multiple imputation with monotone regression of total scores	 MIdataset1 (N=200, Seed=5748941) Imputation variables: Rutgeerts score at Week 48 Ancillary variables: Treatment group, and history of primary non-response to at least one approved ADT (Yes, No), clinical remission status at baseline (CDAI < 150, CDAI ≥ 150), region (North America, Western Europe, rest of world) and number of prior surgeries (1 surgery versus > 1 surgery, with the qualifying surgery counting as 1 surgery)

 Table 8:
 Multiple Imputation Methods for Rutgeerts Score at Week 48

The number and percentage of participants who experienced any ICE prior to Week 48 will be summarized by the type of ICE.

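### Treatment policy for ICE 5 and 6 lacks the Week 48 data it needs, and imputing the gap from the randomised arm may overstate the guselkumab effect by a few points

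*Protocol*

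**What the plan says.** - **Estimand.** SAP 5.3.2.1 sets the rule for ICE 5 and 6 as follows: "treatment policy strategy will be used and considers the occurrence of ICE category 5 and 6 is irrelevant in defining the treatment effect" (likewise Protocol 9.4.2). ICE 6 is "Discontinuation of study intervention due to reasons other than those in ICE 3 or 5", so it includes adverse events other than worsening Crohn's disease. Post-discontinuation values are used where they exist.
- **Follow-up after stopping.** Protocol 7.1: "participants discontinuing study intervention are encouraged to complete study visits through the next 12 weeks, at which time an early termination visit" must be performed. Protocol 4.4 lets such participants count as completers "if they have completed an early termination visit which should occur approximately 12 weeks after the last" dose.
- **Endoscopy at early termination (ET).** Protocol 4.1 says participants "will return for an early termination visit at least 12 weeks after study intervention discontinuation", and then says of the same visit: "This visit will include a video ileocolonoscopy at the time of discontinuation". SAP 1.2.1 repeats both statements. Participants with recurrence already shown are exempt.
- **Missing data.** SAP 5.3.3.1: "Multiple imputation will be used for imputing missing data under the assumption that the data are MAR". Table 8 imputes the Week 48 Rutgeerts score from treatment group, history of primary non-response to an advanced therapy, and the three stratification factors. It has no discontinuation term and no post-baseline variable.
- **Supporting analyses.** SAP 5.3.5.1 plans a tipping-point analysis on the primary estimand. SAP 5.3.2.2.1 and 5.3.3.2.1 plan a supplementary estimand in which every ICE, and any remaining missing status, counts as recurrence.

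**The concern.** A treatment-policy estimand asks what happened by Week 48 whether or not drug was continued. For most early stoppers the plan does not collect that outcome. It fills the gap with a model that cannot tell on-drug from off-drug participants, and the guselkumab participants who do have Week 48 scores are mostly still on guselkumab.

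A recurrence found at the ET endoscopy counts, because the endpoint is recurrence prior to or at Week 48. A negative ET endoscopy has no stated use: its owner is imputed like anyone else in the arm. If protection wanes after stopping, the primary analysis would report something nearer an on-treatment effect under a treatment-policy label.

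**Working it through.** **Inputs.** Protocol 9.2 gives 185 per arm, two-sided alpha 0.05, and recurrence of 50% on placebo and 30% on guselkumab. It also gives 15% annual dropout, stated with the disease-recurrence power assumptions. The share *d* of an arm with ICE 5/6 and no Week 48 outcome, and the off-drug risk, are not in the documents; both are assumptions here.

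**The plan's own figure.** Power = Φ{(Δ − 1.96·√[2p̄(1−p̄)/n]) / √[(p₀(1−p₀)+p₁(1−p₁))/n]}. For 50% vs 30%, n = 185: (0.20 − 1.96×0.0509)/0.0499 = 2.01, so power is 97.8%. Protocol Table 5 gives 97.7%.

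**Who is affected.** An ET visit 12 weeks after stopping falls before Week 48 for stops before Week 48 − 12 = 36. Protocol 7.1 lets an ET visit due within 4 weeks of a scheduled visit replace it, which moves the limit to about Week 36 − 4 = 32.

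**Upper bound.** Suppose every stopper's outcome is missing, ET endoscopy adds nothing, and stoppers recur at the full 50%. The true guselkumab rate is 0.30(1−d) + 0.50d, while MAR imputation returns about 0.30. The overstatement is 0.20d.

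| d | True guselkumab rate | True difference | Overstatement | Power at true difference |
|---|---|---|---|---|
| 5% | 31.0% | 19.0 | 1.0 | 96.4% |
| 10% | 32.0% | 18.0 | 2.0 | 94.4% |
| 13.9% | 32.8% | 17.2 | 2.8 | 92.3% |
| 20% | 34.0% | 16.0 | 4.0 | 88.0% |

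The 13.9% row is 15% a year carried to Week 48: 1 − 0.85^(48/52). With off-drug risk of 40% instead of 50%, that row gives 0.10 × 13.9% = 1.4 points and 95.7% power.

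**Counting positive ET endoscopies.** Use constant hazards λp = ln 2/48 and λg = −ln 0.7/48, last dose at week s, and ET endoscopy at s + 12. Let *r* be the probability of recurrence by ET. The plan then gives a stopper r + (1−r)×(arm rate). The truth is r + (1−r)q, where q is the risk from ET to Week 48.

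- s = 0, placebo hazard after stopping, d = 13.9% in both arms: r = 1 − 2^(−0.25) = 0.159 in each arm. Imputed stopper risk is 0.580 on placebo and 0.411 on guselkumab; the true risk is 0.50 in both. Estimated difference = 0.861×0.20 + 0.139×(0.580 − 0.411) = 19.6 points, against a true 17.2. Bias is +2.3 before rounding.
- s = 24, same assumptions: estimated 19.9, true 18.5, bias +1.4.
- Drug hazard persists, equal dropout of 13.9%, s from 0 to 24: bias +0.3 to +0.5.
- Drug hazard persists, 22% guselkumab vs 13% placebo dropout, s from 0 to 24: bias −0.3 to −1.0. At s = 24, imputed stopper risk is 0.703 on placebo and 0.464 on guselkumab. The estimate is (0.87×0.50 + 0.13×0.703) − (0.78×0.30 + 0.22×0.464) = 19.0, against a true 20.0.

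The reversal arises because an ET-negative stopper is given a fresh 48-week risk on top of time already survived. That inflates the rate more in the arm with more stoppers. The 22% and 13% are the adverse-event discontinuation rates quoted in Protocol 2.2.2 for the cited infliximab trial, used only as a range.

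**The case against.** The strongest reply is that the plan already covers this scenario. The tipping-point analysis uses the primary estimand after applying the ICE rules and varies missing outcomes independently by arm, including guselkumab worse than placebo. At 13.9% missing there are about 0.139 × 185 ≈ 26 guselkumab participants in question. MAR puts about 8 recurrences among them (0.30 × 26) and full reversion puts 13 (0.50 × 26); both lie inside the grid. This stands: robustness of significance is examined. But a grid is not an estimate matched to the estimand, and the all-ICE composite answers a different question by counting every discontinuation as recurrence.

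Second, the affected group is limited. Surgery, prohibited Crohn's medication, stopping for lack of efficacy or worsening disease, and cross over already count as recurrence. Late stops can still give near-Week-48 data, and Protocol 2.2.2 expects fewer adverse-event discontinuations than with infliximab. This also stands, and is why the table is an upper bound. Its full 50% is harsh for someone protected for months: under constant hazards, stopping at Week 24 gives 1 − √(0.7×0.5) = 41%.

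Third, the conflict over ET endoscopy timing is partly a drafting matter. The Schedule of Activities footnote and Protocol 4.4 and 7.1 agree on about 12 weeks for the visit. It is secondary, but it bears on how much off-drug risk the endoscopy can show.

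**Conclusion.** The mismatch is established by the documents: treatment policy for ICE 5 and 6, follow-up that ends about 12 weeks after stopping, and an imputation model blind to discontinuation and to ET findings.

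A reader might infer that the effect is certainly overstated and the analysis biased toward guselkumab. The documents do not support that, because they give neither the ICE 5/6 rate nor the off-drug risk. Overstatement is the likelier direction if risk returns toward placebo. Its size is at most 2.8 of 20 points at the plan's own dropout, if every dropout is ICE 6 with a missing outcome and full reversion. It is about 1.4 to 2.3 points once positive ET endoscopies count, for last doses between Weeks 0 and 24 and equal dropout. Power at 2.8 points is still 92%, above the planned 90%. It falls to 88% only if 20% of the guselkumab arm stop for these reasons with every outcome missing. With a persisting drug effect and more dropout on guselkumab, the effect would be understated by up to about 1 point.

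SAP section 1 states that four participants were enrolled and the planned analyses no longer apply. No reported result is affected.

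**What to change.** 1. In SAP 5.3.3.1 and Table 8, add to the imputation model discontinuation status, the ET Rutgeerts score when below i2a, and the last or ET CDAI. State how these terms are coded for participants without an ET visit, and that an ET score of i2a or above by Week 48 is an observed recurrence. Endoscopy and CDAI are already scheduled at ET; fecal calprotectin is not, so it adds little for early stoppers.
2. Pre-specify one reference-based analysis, reported beside the MAR result: guselkumab participants with ICE 5/6 and no Week 48 endoscopy are imputed from the placebo arm. This is needed even with step 1, because a discontinuation term can be estimated only from the probably few stoppers who do have Week 48 scores.
3. Reconcile the statements in Protocol 4.1 and SAP 1.2.1 on when the ET visit and its ileocolonoscopy take place.

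The cost is SAP text and one extra imputation run. The planned estimate might come out slightly less favourable to guselkumab.
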